## **8.5 Blinding**

Data analysts will be blinded to treatment allocation.

## **9.0 TREATMENTS**

### **9.1 Usual care**

Participants allocated to usual care (Strategy B) will receive instructions in managing their acute LAS accordingly to the S.O.P. at the site (Appendix 1). These guidelines consist of advice provided by the physician at work in; Rest, Ice, Compression and Elevation. Avoiding new stretches/ sprains for a few months after the injury is advised and gradually putting more weight on the ankle, progressing to running and twisting.

## **9.2 Physiotherapy**

Participants allocated to ESP physiotherapy (Strategy A) will receive instructions on how to manage their acute LAS and a written homebased exercise program by an ESP physiotherapist. The instructions on how to manage their acute LAS will consist of written and oral advice. The protocol consists of advice in accelerated weight bearing, already at discharge. It is advised to bear weight and exercise with pain up to, but not exceeding, VAS 5. The written homebased exercise program should be initiated at discharge from the hospital. When patients are experiencing pain exceeding VAS 5 they will follow the same guidelines as the usual care group consisting of Rest, Ice, Compression and Elevation.

Compression, with an elastic bandage, is administered in the ED and instructions on how to apply and manage the bandage correctly, will be given. The bandage should be worn all day, including at night for 3 weeks. The elastic bandage should also be worn as protection when performing exercises and activities that increases the risk of reinjury for a minimum of 3 month after injury.

### **9.2.1 ESP physiotherapy**

An ESP Physiotherapist is a clinical physiotherapy specialist with an extended scope of practice. This implies working beyond the recognized scope of physiotherapy practice, for example requesting investigations e.g. X-rays; using the results of investigations to assist clinical diagnosis and appropriate management of patients; and referring to other professionals. The ESP physiotherapist will have a minimum of 2 years of relevant clinical experience in assessment, diagnosing and treating of patients with minor musculoskeletal injuries. The ESP physiotherapist has taken or are currently enrolled in supplementing their basic professional training with additional courses in musculoskeletal physiotherapy.

### **9.2.2 Exercise program for the physiotherapy group**

The exercise program from baseline to 4 weeks follow-up will consist of ankle rehabilitation exercises focusing on walking with full weight bearing, neuromuscular training, balance training, muscle strengthening and jumping. The participants will be asked to perform the exercises on a daily basis. The exercises should be performed with pain up to but not exceeding 5 on an 0-10 VAS pain scale. If the patient experience VAS pain  $\geq 6$  he/she should follow the standard guidelines of rest, ice, compression and elevation. The patient will receive information on how to perform the exercises by the ESP physiotherapist and an exercise program will be 16

handed out in the ED (Appendix 2). A link will be sent to the participants with the same exercise program including online videos describing the exercise in detail.

### **9.3 Concomitant Therapy**

Participants will be asked to register the type and frequency of any concomitant therapy. There will be no restrictions in concomitant therapy.

## **10.0 OUTCOME ASSESSMENTS/VARIABLES**

### **10.1 Primary Outcome**

#### **10.1.1 Lower extremity functional scale**

The primary outcome measure is the change from baseline in the Lower extremity functional scale (LEFS) assessed at 4 weeks after randomization. LEFS will also be assessed at 1, 2 and 3 weeks, and 3, 6 and 12 months, these timepoints will be regarded as secondary outcomes.

The Lower extremity functional scale is a self-completed questionnaire providing a total score based on the patients subjective ankle function. The scale consists of 20 functional leg activities, each scored on a five point scale (0 impossible, 4 no difficulty), giving a minimum score of 0 (worst) to 80 (best). The questionnaire will be translated into Danish using a dual-panel approach before trial start. The LEFS will be scored online by the trial participant. This approach avoids the requirement for follow-up visits in a clinic.

### **10.2 Secondary outcomes**

The following secondary outcomes will be measured, at baseline and the 1, 2, 3 and 4 weeks, and 3, 6 and 12 months follow-ups, unless stated otherwise. All of the secondary outcomes will be scored online by the trial participant. This approach avoids the requirement for follow-up visits in a clinic.

#### **10.2.1 Pain at rest and with activity, assessed using a visual analogue scale (VAS)**

The pain VAS is a unidimensional measure of pain intensity, which has been widely used in diverse adult populations. The scale is a continuous scale comprised of a horizontal line,

anchored by 2 verbal descriptors, one for each symptom extreme (0 no pain, 10 the worst imaginable pain). We will measure pain VAS at rest and pain VAS with activity.

### **10.2.2 Foot and ankle ability measure (FAAM)**

The FAAM scale is a region-specific outcome instrument divided in two separate subscales, the FAAM activities of daily living (adl) and the FAAM Sports subscales. Evidence of validity to support the use of the FAAMadl and FAAMsport is available in individuals with a wide array of ankle and foot disorders. The questionnaire will be measured at 1, 2, 3 and 4 weeks, and 3, 6 and 12 month follow-ups and used in secondary analysis. The questionnaire will not be measured at baseline. The questionnaire will be translated into Danish using a dual-panel approach before trial start.

### **10.2.3 The Cumberland ankle instability tool (CAIT)**

The CAIT is a simple, validated, and reliable tool to measure severity of functional ankle instability. The CAIT consists of 9 questions that are answered separately for the right and left ankle. It is scored on a 30-point scale, with lower scores indicating decreased stability. The minimal clinically important difference (MCID) for patients with chronic ankle instability is  $\geq 3$  points. The questionnaire will be translated into Danish using a dual-panel approach before trial start.

### **10.2.4 Reinjury rates**

Reinjury rates will be recorded during follow-up assessments at weeks 1-4 and 3-12 months. We endorse the definition of an ankle sprain as: *“An acute traumatic injury to the lateral ligament complex of the ankle joint as a result of excessive inversion of the rear foot or a combined plantar flexion and adduction of the foot. This usually results in some initial deficits of function and disability”*. Reinjury will not be considered as a stopping rule for further participation in this study. Reinjuries will be measured at 1, 2, 3 and 4 weeks, and 3, 6 and 12 month follow-ups and used in secondary analysis.

### **10.2.5 Quality of life (EQ-5D-3L)**

The EQ-5D-3L is a measure of current health status developed by the EuroQol Group for clinical and economic appraisals. The questionnaire consists of five questions assessing five

dimensions (mobility, self-care, usual activities, pain/discomfort and anxiety/depression). Each dimension is rated on three levels: no problems, some problems and extreme problems.

#### **10.2.6 Global perceived effect (GPE)**

Perceived effect of treatment will be measured using a transition questionnaire (TRANS-Q) on which the participants will answer if their current LAS-related health status is “unchanged”, “worse” or “better” compared to their pre-LAS status. An “unchanged” equals a transition score of 0. If the participant answers “worse”, he/she is asked to rate the degree of worsening on a 7 point Likert scale, and the corresponding scores range from -1 to -7. If a participant answers “better”, he/she is asked to rate the degree of improvement on a 7 point Likert scale, and the corresponding scores range from 1 to 7.

#### **10.2.7 Patient acceptable symptom state (PASS)**

The PASS is the value beyond which patients consider themselves well. Patients’ opinions of their state will be recorded by answering “Yes” or “No” to the question: “Taking into account all the activities you have during your daily life, your level of pain, and also your functional impairment, do you consider your current state is satisfactory?”.

#### **10.2.8 Analgesic use**

The participants self-reported use of analgesics will be collected at baseline and at follow-up week 1-4. Participants will be asked to note their use of analgesic drugs within the week before baseline and the follow-up.

### **10.3 Data collection methods**

For consenting patients, we will at Baseline collect data on age, height, body weight, previous lateral ankle sprain, limb dominance, injured limb left/right, time since injury, education, employment, patient’s contact details (Appendix 4). The information will be derived using an online platform on an Ipad available in the emergency department. Baseline data will be collected after randomization, but before treatment, E.g. in the waiting room after medical imaging.

The questionnaires will be sent to the participants in the study at 1, 2, 3 and 4 weeks and 3, 6, and 12 months. The data will be collected using an internet-based platform (Easytrial), with personal links sent to the participants on the day the window for follow-up opens. The window for completion of data registration will be small during the first 4 weeks allowing only a  $\pm 2$ -day registration window. At the 3, 6 and 12-month follow-up, reminders will be sent one and two weeks before and one week after the follow-up date. This will give a window of 4 weeks for completion of the assessments. See Appendix 7 for a copy of the covering letters.

To improve response rates participants will be offered the option of completing the questionnaires in paper versions to be returned by post. We will send pre-notification messages/emails/letters.

## **11.0 DISCONTINUATION**

### **11.1 Participant withdrawal**

As this is a study performed in the emergency department, participants will not be able to have a 24-hour consideration period before inclusion in the study. We consider the study and its procedures to be justified from a health research ethics perspective. There are no risks or predictable harms associated with this approach.

A participant is advised to contact the investigators by telephone if they wish to withdraw from the study. A participant will be able to withdraw at any time point throughout the study period without this impacting on any future investigations and/or treatments.

If a participant withdraws from the study, the primary and secondary outcomes are sought collected before discontinuation.

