### **13.3 Study Population definitions**

#### **13.3.1 Intention to treat population (ITT)**

The ITT population consists of all randomized patients regardless of whether the patient received study intervention or failed to comply with the study protocol, in the treatment group to which the participant was assigned (see Figure 2).

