#### **13.3.3 As-observed population (AO)**

The AO population consists of participants who has the outcome of interest assessed at a given time point of interest (i.e. no imputation of missing data will be done).

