## **13.6 Primary analysis**

### **13.6.1 Primary outcome analysis**

The primary endpoint is the change from baseline in the lower extremity functional scale at the 4-week follow-up. The primary analysis will be done on the ITT population.

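### Section 11.1 seeks outcomes only before a participant leaves, so a withdrawal before day 26 gives no week-4 LEFS, although one short questionnaire could still be offered then

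*Combined protocol and SAP*

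**What the plan says.** On withdrawal, section 11.1 of the combined protocol and SAP says: "A participant will be able to withdraw at any time point throughout the study period". It advises the participant to telephone the investigators, and adds: "If a participant withdraws from the study, the primary and secondary outcomes are sought collected before discontinuation".

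On the endpoint, section 13.6.1 says: "The primary endpoint is the change from baseline in the lower extremity functional scale at the 4-week follow-up". Section 10.1.1 agrees and gives every other LEFS assessment a lower rank: "LEFS will also be assessed at 1, 2 and 3 weeks, and 3, 6 and 12 months, these timepoints will be regarded as secondary outcomes". Section 12.2 allows ±2 days around each of the four weekly assessments. Section 10.3 has the personal link sent on the day the window opens.

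On the analysis set, section 13.3.1 says: "The ITT population consists of all randomized patients regardless of whether the patient received study intervention or failed to comply with the study protocol". Sections 13.4 and 13.6.1 base the primary analysis on this population. The only statement about imputation is in section 13.3.3, for the as-observed population: "no imputation of missing data will be done".

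On logistics, treatment is a single session in the emergency department (section 7.1). There are no trial visits and follow-up is online (section 12.1), with paper forms by post as an option (section 10.3).

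**The concern.** The ITT analysis needs a week-4 LEFS from everyone randomized. The withdrawal rule asks for data at or before the exit and then stops. For anyone who leaves before the week-4 window opens, the value that the primary analysis needs does not yet exist, and nothing in the plan tries to obtain it later.

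In many trials little could be done about this. Here there is no continuing treatment contact and no clinic visit to escape, so leaving the trial mostly means no longer answering questionnaires. Some people who are tired of weekly forms might still answer one short form at week 4. The telephone call described in section 11.1 is the natural moment to ask. As written, the protocol misses that chance, and it does not separate a wish to stop the questionnaires from a wish for no further contact.

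At stake are some primary endpoint values, and with them some precision and some protection against bias from missing data.

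**Working it through.** **1. When the primary value can exist.** Input: week k is day 7k ± 2 after randomization (sections 10.1.1 and 12.2).

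| Assessment | Window (days) | Status of LEFS |
|---|---|---|
| Week 1 | 5–9 | secondary |
| Week 2 | 12–16 | secondary |
| Week 3 | 19–23 | secondary |
| Week 4 | 26–30 | primary |

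**2. What an exit LEFS can serve.**
- Exit on days 1–25: never the primary endpoint. Of these 25 days, 3 × 5 = 15 fall in a week-1, week-2 or week-3 window and give a valid secondary value. The other 10 (days 1–4, 10–11, 17–18 and 24–25: 4 + 2 + 2 + 2) fall in no window.
- Exit on days 26–30: the exit LEFS can itself be the week-4 value.
- Exit after day 30: the week-4 assessment has already passed, so the rule cannot cost the primary endpoint.

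The gap is therefore confined to withdrawals before day 26.

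**3. Whether another section fills the gap.** Sections 10.3, 12.1, 12.2, 13.3 and 13.6 contain no week-4 contact after withdrawal and no rule for an absent week-4 value in the ITT analysis.

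**4. The plan's own sample size.** Inputs from sections 13.1, 13.5 and 8.4: difference 9, SD 19, power 90%, two-sided alpha 0.05, ratio 1:1.

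n per group = 2 × (1.960 + 1.282)² × 19² / 9² ≈ 93.7, which rounds up to 94. This reproduces the stated figure.

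**5. What missing week-4 values do to power.** Power = Φ(9 / (19 × √(2/n)) − 1.960), with 226 randomized, or 113 per arm. Section 13.1 describes the 9-point difference at 6 months. Applying it and the SD of 19 to week 4 is an assumption.

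| Without week-4 LEFS | n per arm | Power |
|---|---|---|
| 0% | 113 | 94.5% |
| 20% | 90.4 | 89.0% |
| 30% | 79.1 | 84.6% |

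**6. Bounds on what an offer could recover.** The plan allows for 20% loss in all, which is 226 × 0.20 = 45.2 participants. If none of that loss is withdrawal before day 26, or nobody accepts, the offer recovers nothing. If all of it is and everybody accepts, power moves from 89.0% to 94.5%. Neither extreme is realistic. The documents give no split of the 20% by time, by arm, or between withdrawal and non-response, so nothing narrower can be derived.

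**The case against.** **The rule does not cause the loss.** The week-4 value goes missing because the participant leaves, and sections 11.1 and 15.1 protect the right to leave at any time. This stands. A person who refuses further contact cannot be followed, so any remedy must be an optional offer.

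**An exit value is worth having.** On 15 of days 1–25 it serves a secondary time point, and a value in hand may be better than one promised for later. This stands too, and it is why the exit LEFS should be kept and the week-4 form offered in addition.

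**Stopping the exercises is not withdrawal.** Section 13.3.1 keeps participants who do not comply, and section 10.2.4 says reinjury does not end participation. Section 11.1 applies only to those who leave the study. This stands.

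**The larger gap is the missing rule for absent week-4 data.** Such a rule would cover every cause of loss. This is true, but it governs the analysis of data already lost. It does not collect any.

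**A stronger reading is tempting.** A reader might infer that an exit LEFS, which section 11.1 calls a primary outcome, will be entered as the week-4 value. Because recovery is under way, that would make the arm with more early withdrawals look worse. The documents do not support this. Section 12.3 uses the same phrase for what is collected at baseline, where it can only mean the instruments. Sections 10.1.1, 12.2 and 13.6.1 fix the endpoint at week 4, and no section carries a value forward. Nor does any section say that the exit LEFS is taken on the very day of withdrawal. The text says only that it is sought beforehand.

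**Conclusion.** The point holds as a cheap improvement to data collection. A participant who withdraws before day 26 gives no primary endpoint value under section 11.1, and the plan makes no attempt to obtain one at week 4, although remote follow-up makes that easy to offer.

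The size cannot be computed from the documents. The number of withdrawals before day 26 is not given, and neither is the share who would accept a final questionnaire. The power figures show only the range that the plan's 20% allowance would permit, and they assume that the sample-size inputs apply at week 4.

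No bias figure is offered. One would need a recovery slope, withdrawal rates by arm, exit days, and the use of exit values as week-4 values. The documents give none of the first three and do not plan the fourth. Only Strategy A includes a home exercise programme, so early withdrawal could differ by arm, but that is a possibility and not a documented fact.

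**What to change.** Rewrite section 11.1 so that a participant who wishes to stop:

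- (a) is asked for LEFS at withdrawal, recorded with its actual date and used only for a scheduled time point in whose window that date falls; and
- (b) is also offered, as an optional alternative to full withdrawal, one final LEFS in the week-4 window (days 26–30), online or on paper.

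Record stopping the questionnaires separately from withdrawal of consent to any further contact, so that the two can be reported and analysed apart.

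The cost is one rewritten paragraph, one more option on the withdrawal form and one later contact, which some participants will decline or not answer. Because (a) does not depend on (b), nothing collected today is given up. Treatment, sample size and assessment schedule are unchanged. The ethics committee would need to be told of the change, as section 15.7 already provides. How the ITT analysis treats a week-4 value that is still missing needs its own rule in section 13, which this change does not replace.

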### **11.2 Discontinuation of clinical sites**

The Sponsor has the right to terminate the participation of a clinical site at any time. Reasons may include the following, but are not restricted to:

- The incidence of events at the site that indicate a potential health hazard to participants and which is not considered sporadic (i.e. events could be expected to occur at other sites as well).
- Unsatisfactory participant enrolment at the site.
- Unsatisfactory data completeness at the site.

- The incidence of protocol violations at the site which is not considered sporadic or very severe (i.e. events could be expected to occur at other sites as well).

### **11.3 Discontinuation of Entire Study**

The Sponsor has the right to terminate this study at any time. Reasons may include the following, but are not restricted to:

- The incidence of events in this or other studies that indicate a potential health hazard to participants.
- Unsatisfactory participant enrolment.

## **12.0 STUDY PROCEDURES**

### **12.1 Trial related clinical visits**

There will be no trial-related clinical assessments. Follow-up will be done only via internet-based assessments.

### **12.2 Assessment windows**

The assessment windows are as follows:

- Baseline measurements will be taken after randomization but before treatment in the ED.
- Outcome assessment at 1, 2, 3 and 4 weeks can be taken within  $\pm 2$  day for the scheduled assessment
- Outcome assessments at 3, 6, and 12 months can be taken within  $\pm 2$  weeks before or after the scheduled assessment.

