### **12.3 Baseline assessment**

Baseline tests and procedures must be performed and reviewed before allocation. The following information/assessments will be collected at the baseline visit:

1. Inclusion/exclusion criteria review
2. Collection of baseline information (Appendix 4)

3. Collection of primary and secondary outcomes
4. Randomization

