## **13.0 DETERMINATION OF SAMPLE SIZE AND STATISTICAL ANALYSIS PLAN**

### **13.1 Determination of Sample Size**

The study will be powered to detect a difference in change of 9 points between the two groups in the primary outcome (LEFS) from baseline to 6 months follow-up. The 9 point change has previously been recommended and applied in similar studies as the minimal clinically important difference in LEFS. To detect this difference, we will need 94 patients in each group (assuming a common SD of 19, power = 90%, alpha level = 0.05). We plan to recruit 226 patients to account for loss to follow-up (20%).

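### Baseline LEFS, one of the two terms of the primary change score, is set both after randomization (10.3, 12.2) and before allocation (12.3); the first order can bias the treatment effect

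*Combined protocol and SAP*

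**What the plan says.** Three sections of the protocol set the time of the baseline assessment.

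- Section 12.2 (Assessment windows): "Baseline measurements will be taken after randomization but before treatment in the ED".
- Section 10.3 (Data collection methods): "Baseline data will be collected after randomization, but before treatment".
- Section 12.3 (Baseline assessment): "Baseline tests and procedures must be performed and reviewed before allocation". Its numbered list puts "Collection of primary and secondary outcomes" at item 3 and randomization at item 4.

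On the endpoint, Section 13.6.1 says: "The primary endpoint is the change from baseline in the lower extremity functional scale at the 4-week follow-up". Section 10.1.1 adds: "The LEFS will be scored online by the trial participant". On blinding, the whole of Section 8.5 is: "Data analysts will be blinded to treatment allocation". Section 7.1 describes one arm managed by an ESP physiotherapist with a home exercise program and the other advised by a physician.

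**The concern.** The first two rules and the third cannot both be followed, and nothing in the text says which governs. With two sites, each could adopt a different order and claim compliance.

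The 10.3/12.2 order also carries a risk of its own. LEFS is a subjective rating. If a participant has learned the assigned arm, or staff who influence the answers have, the baseline rating may respond to that knowledge. The baseline is then no longer protected by randomization, and a difference between arms at baseline need not be chance. Because the endpoint subtracts the baseline, that difference becomes part of the estimated effect. More patients would make the biased estimate more precise, not less biased.

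There is a second, smaller risk. Someone who leaves after randomization but before completing the form has no baseline and so no change score, and such departures could differ by arm.

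**Working it through.** **Side by side.** Sections 10.3 and 12.2 give randomize, then baseline, then treat. Section 12.3 gives eligibility review, baseline information, outcome collection, then randomize. Section 10.3 lists mainly demographic items, so the rule reaches LEFS through the general wording of 12.2 and through item 3 of 12.3, which places the primary outcome in the baseline visit.

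**Inputs, from Section 13.1 unless noted.** Target difference in change 9 points; common SD 19; 94 per group; power 90%; alpha 0.05; tests two-sided (13.5); allocation 1:1 (8.4). Section 13.1 ties these figures to 6 months while the primary endpoint is at 4 weeks. That is a separate matter; they are used here because they are the only planning figures given.

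**The plan's own figure.** n per group = 2 × (1.960 + 1.282)² × 19² / 9² = 93.7, rounded up to 94. Power at 94 per group is 0.901 by the normal approximation. The stated 94 is reproduced.

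**How a shift passes through.** Suppose knowledge of the allocation lowers reported baseline LEFS by s points in one arm relative to the other and leaves the 4-week score untouched.

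- Difference in change = difference at 4 weeks − difference at baseline = true effect + s.
- A shift the other way gives true effect − s.

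**Size.** SE = 19 × √(2/94) = 2.77. With no true effect, the two-sided rejection rate is Φ(−1.96 − s/SE) + 1 − Φ(1.96 − s/SE). The last column takes a true effect of 9 with the shift running against the intervention. The values of s are assumptions, since the documents give none.

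| s (points) | Share of 9-point target | Type I error | Power |
|---|---|---|---|
| 0 | 0% | 5.0% | 0.901 |
| 1 | 11% | 6.5% | 0.823 |
| 2 | 22% | 11% | 0.714 |
| 3 | 33% | 19% | 0.581 |

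**With baseline adjustment.** The plan names no model, so ANCOVA was checked too. Assume equal SDs at baseline and 4 weeks and correlation r between them. Then:

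- bias = r × s
- SE = [19/√(2(1 − r))] × √(1 − r²) × √(2/94)

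At s = 3:

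| r | Bias (points) | SE | Type I error |
|---|---|---|---|
| 0.3 | 0.9 | 2.23 | 6.9% |
| 0.5 | 1.5 | 2.40 | 9.6% |
| 0.7 | 2.1 | 2.56 | 13.0% |

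Adjustment shrinks the bias to 0.3–0.7 of the shift but does not remove it.

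**The case against.** The contradiction is not in dispute. The case against concerns how much can be built on it.

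- **Knowledge of the arm is inferred.** The protocol does not call the trial open-label, and being randomized is not the same as being told. If the arm were still concealed when the form is completed, a baseline taken before treatment would not be distorted this way. This stands as a limit: the claim is that the order can bias the result, not that it will. But no section provides such concealment.
- **The flow charts could not be read.** Figures 1 to 3 might show the intended order or the moment of disclosure. They could not remove the conflict between the written sections.
- **The shift is assumed.** Nothing in the documents supports its size or direction, or shows that it is not zero, and the LEFS form asks about difficulty today rather than expected benefit. This stands. The error rates illustrate sensitivity and do not predict what will happen.
- **The full pass-through applies only to an unadjusted change score.** This stands, and the ANCOVA figures show the reduction. It also means that adjustment, though imperfect here, would be less biased than the raw change score.
- **ITT keeps everyone randomized.** Section 13.3.1 does so, which makes a missing baseline a missing-data problem in the primary analysis rather than a formal exclusion. The plan names no method for it. Only the per-protocol set (13.3.2) requires a valid baseline. Departure that differs by arm is a possibility, not something the documents show.

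**Conclusion.** The concern holds and should be fixed. The protocol gives two incompatible rules for when a component of the primary endpoint is measured, and one of them exposes that endpoint to bias.

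The contradiction rests on the text alone. The bias is conditional on the participant, or staff who influence the answers, knowing the arm when the baseline LEFS is completed. That is plausible given Sections 7.1 and 8.5 but is not stated. If it happens, each point of shift moves an unadjusted estimate by one point, or by 0.3 to 0.7 of a point with baseline adjustment under the assumed correlations. For shifts of 1 to 3 points the nominal 5% error rate becomes 6.5% to 19% unadjusted; at 3 points it is 6.9% to 13.0% adjusted. The direction is unknown, so the result could be exaggerated or diluted.

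The priority is high because a contaminated baseline cannot be collected again and analysis can repair it only in part.

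**What to change.** Amend Sections 10.3 and 12.2 to match 12.3. The sequence would be consent, eligibility review, the iPad baseline form including LEFS and the other baseline outcomes, then randomization. Set the electronic system to release the allocation only after the baseline form is submitted, and check that Figures 1 to 3 show the same order. Storing the times of form submission and randomization would let the order be verified for every participant.

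The cost should be small: two sentences in the protocol and a change to the order of steps in the system. This is a judgement, since the documents do not describe how the form fits the flow of the emergency department. A few people may complete the form and then not be randomized. The sample size stays at 94 per group with power 0.901. The expected baseline shift from knowing the allocation becomes zero, so this route no longer moves the error rate from 5%.
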